1.7 Study Design Considerations

E2108 is designed to examine the value of early local therapy for the primary tumor in Arm B versus standard of care in Arm A. Laboratory measurements that involve comparison of pre- and post- local therapy values can therefore only be performed in Arm B. However, the Circulating Tumor Cell (CTC) burden prior to primary site local therapy may be substantially reduced by the preceding induction systemic therapy. Statistical testing of CTC values pre and post local therapy in Arm B may therefore not be feasible. A more robust comparison would be one performed at six months following randomization, where local therapy would be completed in Arm B and the CTC burden would represent the cumulative effects of local and systemic therapy (Arm B) versus systemic therapy alone (Arm A).

2. Objectives

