2.2 Secondary Objectives

Rev. 4/14

- 2.2.1 To compare the time to uncontrolled chest wall disease between patients who receive early local therapy versus patients who receive palliative local therapy
- 2.2.2 To determine whether there is a difference in HRQL between patients who receive early local therapy and those who receive palliative local therapy.
- 2.2.3 To determine whether the absolute value of the CTC burden at six months following randomization will be lower in Arm B than Arm A and whether this value is inversely related to survival.
- 2.2.4 To collect tumor and blood specimens for future exploration of the biological interactions between the primary tumor and metastatic lesions and the effect of primary tumor resection.

3. Selection of Patients

Each of the criteria in the checklist that follows must be met in order for a patient to be considered eligible for this study. Use the checklist to confirm a patient's eligibility. For each patient, this checklist must be photocopied, completed and maintained in the patient's chart.

In calculating days of tests and measurements, the day a test or measurement is done is considered Day 0. Therefore, if a test is done on a Monday, the Monday four weeks later would be considered Day 28.

ECOG-ACRIN Patient No. _____

Patient's Initials (L, F, M) _____

Physician Signature and Date _____

NOTE: All questions regarding eligibility should be directed to the study chair or study chair liaison.

NOTE: Institutions may use the eligibility checklist as source documentation if it has been reviewed, signed, and dated prior to randomization by the treating physician.

Rev. 7/12 **NOTE:** Patients may register (Step 1) at any time from the time of diagnosis of stage IV breast cancer (if eligibility criteria met) to the time when a maximum of 30 weeks of induction systemic therapy has been completed. (Induction systemic therapy includes chemotherapy, endocrine therapy, bone-specific agents, and biologic therapy.)

Rev. 7/13 **NOTE:** Patients must be randomized (Step 2) within 32 weeks after the start of systemic therapy.

Rev. 7/12 **NOTE:** Patients may not be randomized (Step 2) less than 16 weeks after the start of systemic therapy.

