7.1 Therapeutic Parameters

Rev. 2/13

1. Prestudy scans and x-rays used to assess all measurable or non-measurable sites of disease must be done **≤ 8 weeks** prior to the initiation of systemic therapy. If pre-therapy scans were not performed, scans performed within the first 4 weeks of systemic therapy will be accepted. The same window applies to history and physical, Local/Regional assessment, ECOG PS, weight and height.
2. Step 2 CBC (with differential and platelet count) must be done during the **6 weeks** preceding randomization.
3. All required Step 2 chemistries must be done **6 weeks** preceding randomization.
4. Step 2 scans and x-rays used to assess all measurable or non-measurable sites of disease must be done within the **6 weeks** preceding randomization. The same window applies to history and physical, Local/Regional assessment, ECOG PS, weight.

Rev. 4/14

Rev. 7/12,
2/13

Rev. 4/14

Rev. 7/12,
2/13

Rev. 7/12,
2/13, 4/14

	Step 1: Registration	Step 2: At randomization	6 months post randomization	12 months post randomization	18 months post randomization	30 months post randomization	At decision for local therapy (Arm A) ³	Long-Term followup ⁵
History & Physical	X ¹	X ⁴	X ¹²	X ¹²	X ¹²	X ¹²	X ⁴	Q 3 months years 0-2; Q 6 months years 2-5
Local/Regional ¹² Assessment	X ^{1,8}	X ⁴	X ¹²	X ¹²	X ¹²	X ¹²	X ⁴	
ECOG PS ¹²	X ¹	X ⁴	X ¹²		X		X ⁴	
Weight	X ¹	X ⁴	X ¹²		X		X ⁴	
Height ¹²	X ¹							
CT chest/abdomen ^{1,10}	X	X	X		X	X	X ⁴	
Bone scan ^{1,10}	X	X	X		X		X ⁴	
Mammogram ⁹	X	X			X		X ⁴	
Breast Ultrasound ⁹	X	X			X		X	
Pregnancy Test ²	X	X						
QOL assessment ¹¹	X ⁴	X ⁷	X		X	X	X	
CTC Enumeration ⁶		X ⁷	X					
Biological Sample Submissions								See Section 7.2

Rev. 7/12,
2/13

Rev. 4/14

Rev. 7/12

1. CT scans with bone windows or PET CT are allowed instead of CT chest/abdomen and bone scan. If performed at baseline, should be repeated within 6 weeks prior to randomization and during follow-up, if possible. If not possible (e.g. denied by insurance), other appropriate tests can be substituted that will evaluate all prior sites of disease and will address any new signs/symptoms.
2. Urine or serum pregnancy test must be done in women of child-bearing potential < 2 weeks prior to randomization.

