Rev. 7/12 3. In Arm A patients, if a decision is made to deliver palliative local therapy, a complete local-regional assessment must document reason for palliative treatment and must include same imaging tests that were performed at start of systemic therapy, if possible. If not possible, (e.g. denied by insurance), other appropriate tests can be substituted that will evaluate all prior sites of disease and will address any new signs/symptoms.

Rev. 4/14 4. [Deleted in Addendum #2]

Rev. 7/12 5. Patients who are not randomized will be followed for survival for 5 years post registration.

Rev. 7/12 6. Collect only if performed as part of standard clinical assessments and covered by third party reimbursement.

Rev. 7/12, 7/13 7. Collect prior to randomization.

Rev. 4/14 8. Pathology reports confirming diagnosis of breast cancer and, if only one metastatic lesion is present, the metastatic site must be submitted to the ECOG-ACRIN Operations Office - Boston within one month of registration to step 1.

Rev. 4/14 9. Breast imaging studies with mammogram OR ultrasound OR breast MRI measurement are requested at baseline (see 3.1.4 and 7.1 for definition of baseline evaluation). However, if in the judgment of the physician, physical exam provides sufficient documentation of tumor size and T stage, and breast imaging has not been performed in the baseline period, the patient is still eligible. If possible, the same imaging studies should be repeated in the pre-randomization interval (within 6 weeks prior to randomization). If not possible (e.g. denied by insurance), other tests can be substituted that will evaluate the breast and will address any new signs/symptoms. Mammogram and ultrasound may be unilateral (affected side) or bilateral, at physician discretion. Breast imaging is not required if the breast is replaced by tumor or ulcerated in a way that makes breast imaging not feasible. If so, physical exam documentation must reflect this. A physical exam can only be used for pre-randomization evaluation of the breast if imaging is not feasible and tumor is palpable: in this case, physical exam findings describing the tumor must be documented. During follow-up breast imaging studies with mammogram OR ultrasound OR MRI need to be performed.

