8.4 Sample Size

The primary comparison will be an intention-to-treat analysis including all randomized patients. It is expected that the three-year survival in the control arm will be 30%. The primary analysis of survival will be performed using a one-sided logrank test stratified on the stratification factors including marker status and treatment plan, number of involved organ systems, using an overall type I error of 5%. Allowing for the interim analysis plan discussed below, a total accrual of 186 responders and a total information of 110 deaths is planned, to give 85% power

to detect a 19.3% difference in the three-year survival rates (i.e., 49.3 % in the experimental arm). To allow for 15% probability of crossover between two arms (sum of the probabilities of patients on the experimental arm crossing over to the control arm and vice versa), both numbers are inflated by a factor of 1.38 (based on the Lachin-Foulkes correction)(53) to a total accrual of 258 responders and a total information of 152 deaths. Assuming an exponential distribution, this difference corresponds to an improvement in median survival from 21.4 to 33.5 months. Assuming 70% of the recruited patients are eligible and responding, a total of 368 patients will be needed to accrue 258 responders. Assuming an accrual rate of 6 patients per month, 62 months of accrual will be needed. The sample size was computed using seqopr6 (part of the study design library at the ECOG-ACRIN Statistical Office).

Rev. 7/13, 4/14

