Rev. 7/13		Two sample t-test/Wilcoxon test will be conducted to test whether the CTC burden at 6 months after randomization will be lower in Arm B than in Arm A. Cox proportional hazards (PH) model will be used to examine whether patients with lower CTC burden at 6 months after randomization have prolonged survival. The treatment assignment, CTC burden or possibly their interaction will be included in the Cox PH model.
Rev. 7/13		Assuming 60% of the patients would provide their CTC at 6 months after randomization, we would have 155 evaluable patients, with 77 patients per arm. Assuming the standardized difference is 0.339 (difference in mean/standard deviation; e.g. the difference in CTC at 6 months after randomization for the two arms is 1 and the SD is 3), then the given sample size will provide 77% power using a two sample t test with two-sided significance level of 0.20.
Rev. 7/13		A paired t-test/ Wilcoxon test would be used to test whether there is a reduction in CTC burden from randomization to 6 month assessments in Arm B. A Cox PH model will be conducted to evaluate whether a larger reduction in CTC predicts longer survival.
		A two sample t-test/Wilcoxon test would be used to test whether the reduction in CTC in Arm B is larger than Arm A. A Cox PH model will be used to evaluate whether a larger reduction predicts longer survival.

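### Section 8.7 compares 6-month CTC between arms without using the CTC value scheduled before randomization: a valid secondary test that gives up a small, conditional gain in precision

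*Combined protocol and SAP*

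**What the plan says.** Objective 2.2.3 asks whether "the absolute value of the CTC burden at six months following randomization will be lower in Arm B than Arm A". Section 8.7 tests this directly: "Two sample t-test/Wilcoxon test will be conducted to test whether the CTC burden at 6 months after randomization will be lower in Arm B", with Arm A as the comparator. This is the comparison that the section powers: 60% of patients giving a 6-month value, 155 evaluable, 77 per arm, standardized difference 0.339, two-sided level 0.20, stated power 77%.

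The schedule table in Section 7.1 has a row for "CTC Enumeration" with entries at Step 2 and at 6 months. The footnote on the Step 2 entry reads "Collect prior to randomization". The footnote on the whole row reads "Collect only if performed as part of standard clinical assessments and covered by third party reimbursement".

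Section 8.7 does use the randomization value elsewhere. It plans a paired test within Arm B, Cox models of CTC reduction and a second between-arm test: "A two sample t-test/Wilcoxon test would be used to test whether the reduction in CTC in Arm B is larger than Arm A". It names no covariate-adjusted comparison of the 6-month value.

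Section 1.7 explains the preference for the 6-month comparison: the CTC "burden prior to primary site local therapy may be substantially reduced by the preceding induction systemic therapy".

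**The concern.** When an outcome is also measured before randomization, adjusting for that measurement usually sharpens the between-arm comparison at no cost in validity. Here the powered test for a secondary objective leaves the measurement out, and the other between-arm test subtracts it, which is a different and often weaker use of it.

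The comparison is thin: 40% of patients are expected to contribute nothing, and power is below 80% even at a 0.20 level. More observations cannot easily be added, because CTC is recorded only when it is standard care and reimbursed. At stake is some precision in one correlative result.

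**Working it through.** **Inputs from the documents.** 258 randomized patients (Section 8.4); 60% with a 6-month value, 77 per arm, d = 0.339, two-sided alpha 0.20, stated power 77% (Section 8.7).

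**Assumed inputs.** The correlation ρ between randomization and 6-month CTC, and the share f of patients with a 6-month value who also have a randomization value. The documents give neither, so both are shown as ranges.

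**1. The plan's own figure.** 0.60 × 258 = 154.8, which gives the 155. The noncentrality is 0.339 × √(77/2) = 2.10, and the noncentral t distribution gives 79.3% power. Section 8.7 also gives an example with a difference of 1 and an SD of 3, so d = 1/3. That gives 78.3% with a t-test and about 77% with the usual Wilcoxon efficiency of 0.955. The stated 77% is therefore reproduced by the example with a Wilcoxon allowance. The comparisons below use 79.3% so that like is set against like.

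**2. Adjustment keeping all 6-month values.** In a constrained longitudinal model (one common mean at randomization), the variance of the 6-month difference relative to the unadjusted test is 1 / [f/(1 − ρ²) + (1 − f)]. For example, at ρ = 0.3 and f = 0.8: 1 / (0.8/0.91 + 0.2) = 1/1.079 = 0.927. This is equivalent to 77/0.927 = 83 patients per arm, about six more.

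**3. Alternatives.** Complete-case adjustment uses 77f per arm with effect d/√(1 − ρ²). The change test has effect d/√(2(1 − ρ)), computed here as if every patient had both values.

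Power (%):

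| Method | ρ = 0 | 0.1 | 0.2 | 0.3 |
|---|---|---|---|---|
| Planned, unadjusted | 79.3 | 79.3 | 79.3 | 79.3 |
| Constrained model, f = 1 | 79.3 | 79.6 | 80.5 | 82.1 |
| Constrained model, f = 0.8 | 79.3 | 79.6 | 80.3 | 81.6 |
| Constrained model, f = 0.6 | 79.3 | 79.5 | 80.1 | 81.0 |
| Complete case, f = 0.8 | 72.4 | 72.7 | 73.7 | 75.4 |
| Complete case, f = 0.6 | 63.5 | 63.8 | 64.7 | 66.4 |
| Change test | 58 | 61 | 65 | 69 |

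The change test equals the planned test at ρ = 0.5 and is weaker below that. At ρ = 0.5 and 0.7 the constrained model would reach 86.0% and 93.4% (f = 0.8), or 84.5% and 91.2% (f = 0.6).

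**4. Skewed counts.** CTC is a count, so normal theory may flatter the adjustment. A simulation used assumed lognormal-Poisson counts: means 3 and 2, control SD 3.2, f = 0.8, 3,000 runs, simulation error about 0.7 points.

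| Raw correlation | Constrained model, raw counts | t-test | Wilcoxon |
|---|---|---|---|
| 0 | 84.3 | 84.1 | 82.9 |
| 0.20 | 84.1 | 83.5 | 84.6 |
| 0.44 | 88.4 | 84.4 | 84.8 |

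Up to about 0.2 there is no demonstrable gain. At 0.44 the gain over the t-test is 88.4 − 84.4 = 4.0 points. Across roughly 0.3 to 0.5 it is about 2 to 5 points.

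**5. Randomization value missing for reasons tied to its own size.** In normal-data simulations where higher values were more likely to be measured (4,000 runs, ρ = 0.3 and 0.5, about 80% or 60% observed), bias stayed below 0.004 SD. The null rejection rate was 19.8% to 21.2% against a nominal 20%.

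**The case against.** The strongest reply is that nothing is wrong. The planned test is a valid comparison of randomized groups and addresses objective 2.2.3 directly. Section 1.7 gives a reason to expect little from the earlier value, since induction therapy may already have lowered it. On count data the gain disappears at the low correlations this makes plausible; at 0.20 the planned Wilcoxon is nominally ahead of the raw-count model. The normal-theory gain at ρ = 0.3 with 80% available (81.6 − 79.3 = 2.3 points) is no larger than the gap between the recomputed 79.3% and the stated 77%. A Gaussian model on raw counts would also replace a rank test suited to skewed data and add an assumption about missing randomization values.

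Most of this stands. It limits the size of the point and rules out a raw-count Gaussian model as the replacement for skewed data. It does not show that adjustment does harm: under normal theory, power with all 6-month values kept is never below the planned test.

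A reader might infer more than the documents support:

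- **That the planned test is biased or has the wrong error rate.** Randomization protects the unadjusted comparison. Missing 6-month values and deaths before 6 months are a separate limit, and adjustment does not resolve them.
- **That the plan ignores the randomization value.** It enters three other sets of analyses in Section 8.7.
- **That a large amount of power is being lost.** This needs correlations of 0.5 to 0.7, which nothing in the documents supports.

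**Conclusion.** The point holds as a minor matter of efficiency. Section 8.7 leaves a scheduled pre-randomization measurement out of its powered CTC comparison, and the planned change test is no substitute at correlations below 0.5. The normal-theory gain is 0 to about 3 points (79.3% to at most 82.1%) for correlations of 0 to 0.3. The upper end requires every patient to have a randomization value, which the standard-care and reimbursement condition makes unlikely. On raw skewed counts no gain is shown at about 0.2 or below. If the correlation is near zero there is no gain at all.

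These sizes rest on assumed correlations, assumed availability and, for the count check, an assumed distribution. Confidence is medium. The survival analysis is unaffected.

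**What to change.** For objective 2.2.3, specify in advance the 6-month between-arm difference adjusted for randomization CTC:

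- Use a method that keeps patients who have a 6-month value but no randomization value: a constrained longitudinal model, or adjustment with the missing baseline set to the mean pooled over both arms. Do not use complete-case adjustment, which has less power than the planned test over the correlations of 0 to 0.3 when 80% or 60% have a randomization value.
- If the counts are skewed, do this on the log(count + 1) or rank scale, in keeping with the plan's own Wilcoxon option. Report the mean difference on the absolute scale alongside, since that is what the objective names.
- Keep the planned unadjusted t-test/Wilcoxon as a reported sensitivity analysis.
- Adjusting also for the stratification factors used in the primary survival test is optional; no gain is claimed for it.

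The cost is SAP wording and slightly more programming, with no new visits or samples. Section 8.6 already plans a mixed model for HRQL, though without a common mean at randomization, so the type of model is familiar but would need its own specification. The downside is a modelling assumption about missing randomization values. Because that value is taken before assignment, its absence should not depend on arm.

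### The CTC reduction models in Section 8.7 omit the randomization count, so they mix starting level with residual burden, and the Arm B pre/post test is one that Section 1.7 doubts

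*Combined protocol and SAP*

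**What the plan says.** - Section 1.7 (Study Design Considerations) says that "the Circulating Tumor Cell (CTC) burden prior to primary site local therapy may be substantially reduced by the preceding induction systemic therapy". It concludes: "Statistical testing of CTC values pre and post local therapy in Arm B may therefore not be feasible". It then states its preference: "A more robust comparison would be one performed at six months following randomization", comparing the arms.
- Section 2.2.3 follows that reasoning: "To determine whether the absolute value of the CTC burden at six months following randomization will be lower in Arm B than Arm A". It also asks whether that value is inversely related to survival. It does not mention reduction.
- Section 8.7 (Correlative Science (CTC) Power estimate) plans and powers the six-month comparison and gives it a Cox model with treatment, CTC burden and possibly their interaction.
- Section 8.7 then adds a paired t or Wilcoxon analysis to "test whether there is a reduction in CTC burden from randomization to 6 month assessments in Arm B", followed by "A Cox PH model will be conducted to evaluate whether a larger reduction in CTC predicts longer survival". A further paragraph plans to "test whether the reduction in CTC in Arm B is larger than Arm A", followed by a second Cox model with reduction as predictor.
- For the two reduction Cox models, 8.7 gives no covariates, no scale (raw, log or percent), no rule for zero counts and no power. The covariate sentence belongs to the six-month-level model.

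**The concern.** In Arm B, the interval from randomization to six months spans local therapy. The paired test is therefore the pre/post comparison that 1.7 doubts, and 8.7 does not say why it was kept. No stated objective calls for it.

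The Cox models matter more. Reduction is the randomization count minus the six-month count. If the randomization count is not in the model, one number has to stand for both where the patient started and what remains. Objective 2.2.3 concerns what remains. A weak or inverse coefficient on reduction could be reported as evidence against CTC as a marker when it only reflects how the score was built.

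The paired test is also hard to read in either direction. A null result may mean that induction therapy left little to reduce. A fall cannot be credited to local therapy, because systemic therapy continues in Arm B (Section 5.1.2.2).

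**Working it through.** **1. The plan's own figure.** Section 8.7 states 77% power for the six-month comparison, with 77 per arm, standardized difference d = 0.339 and two-sided alpha 0.20. The sample is 0.60 × 258 = 154.8, or 155 patients. Normal approximation: power = Φ(d√(77/2) − 1.282).
- d = 0.339: Φ(2.103 − 1.282) = 79.4%.
- d = 1/3, the plan's example of a difference of 1 with SD 3: Φ(2.068 − 1.282) = 78.4%.
- d = 1/3, Wilcoxon with efficiency 0.955: Φ(2.021 − 1.282) = 77.0%.

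The figure is reproduced to within about two points. Nothing below depends on it.

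**2. Ties and rank order.** Let B be CTC at randomization, F CTC at six months and D = B − F.

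| B | F | D |
|---|---|---|
| 0 | 0 | 0 |
| 50 | 50 | 0 |
| 1 | 0 | 1 |
| 200 | 100 | 100 |

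The first two patients tie. The fourth outranks the third despite a far higher residual count. Patients whose CTC rises score below zero and are separated correctly.

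**3. Dilution.** Suppose the log hazard depends only on F. Then cov(D, F) = ρ·SD_B·SD_F − SD_F². With equal SDs, corr(D, F) = −√((1 − ρ)/2).
- ρ = 0.4: −0.55, so D carries 30% of the variance of F.
- ρ = 0.7: −0.39, so D carries 15%.

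**4. Reversal.** The covariance in step 3 turns positive when ρ·SD_B > SD_F.
- Assumed SD_B = 3, SD_F = 2, ρ = 0.7: 0.7 × 6 − 4 = +0.2. A larger fall then looks harmful.
- Same SDs, log hazard 0.3B + 0.7F: the covariance is 0.3 × 9 + 0.4 × 6ρ − 0.7 × 4 = −0.1 + 2.4ρ. This is positive for any ρ above 0.04.
- SD_B close to 0: D ≈ −F. The sign is right, and D only repeats the six-month value.

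**5. Room for a paired fall in Arm B.** Only patients with CTC above zero at randomization can fall. If 30, 50, 70 or 80% have zero (an assumed range), the 77 pairs leave 53.9, 38.5, 23.1 or 15.4.

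**6. Illustrative simulation.** There were 1,000 runs per setting with 154 patients. Higher CTC was never protective, and all distributions and hazard weights were assumed. The table shows runs in which the unadjusted reduction had the wrong sign.

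| Zeros at randomization / six months | Setting | Wrong sign |
|---|---|---|
| 30% / 50% | ρ = 0.7, raw counts | 72% (only F prognostic); 94% (both) |
| 50% / 65% | ρ = 0.7, raw counts | 53%; 85% |
| 50% / 65% | ρ = 0.7, log scale | 19%; 66% |
| Equal, 50–80% | all settings run | 2–44% |
| 70% / 50% and 80% / 60% | all settings run | 0–8% |

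Across all settings, the reduction score had the right sign with two-sided p < 0.20 in 0–93% of runs. The six-month value did so in 82–100%.

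**7. Why adjustment settles it.** On one common scale, b₁B + b₂F = (b₁ + b₂)B − b₂D. Once B is in the model, the coefficient on D is minus the coefficient on F. The ambiguity then disappears.

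**The case against.** The strongest reply is that the main CTC analysis is already right. Section 8.7 begins with the absolute six-month value, powers only that, and gives it a Cox model with treatment, matching 2.2.3. The reduction analyses are unpowered extras on a marker collected only where it is standard care and reimbursed (Section 7.1, note 6). No stopping rule uses them. Section 8.7 also does not forbid adjusting for the randomization count or using a log scale. All of this stands, and it limits the weight of the point. It does not supply the missing covariate or explain the conflict with 1.7.

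The between-arm test of reduction is a randomized contrast. It remains valid, and 1.7 does not call it infeasible.

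The simulation is also open to challenge. Where only F drives the hazard, it favors F by construction. The wrong-sign range of 0–94% describes the assumptions, not this trial.

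A reader might infer from 1.7 that CTC is close to zero at randomization and that this floor makes the reduction score point the wrong way. The documents support neither step. Section 1.7 says only that the burden may be substantially reduced, and it gives no counts. Step 4 also shows that a true floor at randomization gives the correct sign. Reversal needs wider spread at randomization or a prognostic randomization value.

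**Conclusion.** The point holds, at the level of a secondary correlative analysis. Two parts rest on the text and algebra alone: 8.7 plans Arm B pre/post testing that 1.7 says may not be feasible, and the reduction Cox models as written mix starting level with residual burden.

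Dilution is to be expected if the six-month value drives survival: 15–30% of its variance is retained under equal spread and correlation 0.7 to 0.4, both assumed. Reversal is possible, but its frequency cannot be estimated without a CTC distribution.

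A reader might go further and conclude that the reduction analyses must be deleted or restricted to patients with detectable CTC at randomization. The documents do not require either. Adjustment for the randomization value resolves the ambiguity, and restriction would discard patients. The primary survival analysis is not affected.

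**What to change.** In Section 8.7:
- Replace the two reduction Cox models with one Cox model of six-month CTC, entered as log(CTC+1), with randomization CTC and treatment as covariates, in patients with both samples.
- Label the remaining reduction analyses exploratory.
- State that the Arm B paired test cannot by itself show an effect of local therapy, because systemic therapy continues.
- Reconcile the section with 1.7 and 2.2.3, and keep the six-month level as the main CTC analysis.

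The cost is wording only, since both CTC time points are already in the Section 7.1 schedule. The simple reduction summary for survival is lost. Only patients with both samples contribute: if 60, 80 or 100% of the 155 with a six-month value also have a randomization value (assumed), that leaves 93, 124 or 155. The existing reduction models need both samples too, so they gain nothing in numbers.
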